### **Survivorship**

Hip prosthesis survivorship will be assessed using a Kaplan-Meier analysis.

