**STUDY SPONSOR**

**ZIMMER GMBH  
[name]  
[name]  
SWITZERLAND**

Complete Protocol Title	Randomized controlled study comparing the Taperloc Complete versus the Taperloc Complete Microplasty
Protocol Number	ORTHO.CR.GH60
Short Protocol Title	Randomized controlled study comparing the Taperloc Complete versus the Taperloc Complete Microplasty
Sponsor	Zimmer GmbH, [name]
Manufacturer	Biomet Orthopedics, [name]
Study Device(s)	Taperloc Complete Microplasty PPS-Bonemaster Taperloc Complete Reduced Distal PPS- Bonemaster
Technical Documentation Reference Number	Reference can be found on Post-market surveillance Plan (PMSP)
Study Objectives/Endpoints	
Primary endpoint: Migration of the prosthesis over two years based on RSA data.
 
Secondary endpoints:
 
 
The prevalence of malalignment, incorrect sizing, subsidence and intraoperative fractures at the direct postoperative visit.
 
Survival of the hip prosthesis within 2 years.
 
Clinician based outcomes (HHS and radiological evaluation) and patient based outcomes (HOOS, EQ5D, Oxford Hip score, Forgotten Joint score) at each visit.
 

Indications/Target Population	Subjects with osteoarthritis of the hip scheduled for a primary total hip arthroplasty (THA) who are willing to participate in the study. Subjects have to meet all the in- and exclusion criteria of the study.

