Inclusion/Exclusion Criteria	
Inclusion criteria
 
In order to be eligible to participate in this study, a subject must meet all of the following criteria. These are standard indications for usage of the Taperloc Complete and Taperloc Microplasty stem.
 
Subjects with one of the following indications:
 
 
Non-inflammatory degenerative joint disease including osteoarthritis, avascular necrosis and rheumatoid arthritis.
 
Correction of functional deformity.
 
 
Additional inclusion criteria include:
 
 
Male or female
 
≥ 18 and ≤ 70 years of age
 
Subjects willing to return for follow-up evaluations.
 
Subjects able to read and understand Dutch language.
 
 
Exclusion criteria
 
A potential subject who meets any of the following criteria will be excluded from participation in this study.

	
 
• active Infection (or within 6 weeks after infection)
 
• Sepsis
 
• Osteomyelitis
 
• Uncooperative patient or patient with neurologic disorders who are incapable of following directions
 
• diagnosed Osteoporosis or Osteomalacia
 
• Metabolic disorders which may impair bone formation
 
• Distant foci of infections which may spread to the implant site
 
• Rapid joint destruction, marked bone loss or bone resorption apparent on roentgenogram
 
• Vascular insufficiency, muscular atrophy or neuromuscular disease.
 

Study Design	
A single-centre, randomized controlled post market surveillance study:
 
 
• Group 1: Taperloc Complete PPS-Bonemaster, Reduced Distal, Type 1 Taper (n=25)
 
• Group 2: Taperloc Complete Microplasty Reduced Distal, PPS-Bonemaster, Type 1 Taper (n=25)
 
 
In both groups, the G7 acetabular cup is used with Polyethylene E1 articulation.

Clinical Phase	Post-market
Sample Size	50 subjects in total, 25 study subjects implanted with the study device per cohort.
Length of Study	3 years (1 year of enrolment and 2 years of follow-up)
Materials and Methods	All included patients will be assessed preoperatively and directly postoperative. Follow-up will take place at 6-weeks, 1 and 2 years postoperatively.
Data Collection	Electronic

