## **STATISTICAL METHOD**

Data will be analyzed using the “Statistical Package for the Sciences” version 20.0 or higher. Differences will be 2-tailed tested and alpha is set on 0.05. Data will be presented as per protocol (intention-to-treat) and as treated analysis (treatment eventually received).

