### **Descriptive analysis**

Descriptive analysis will be performed to report baseline characteristics and outcome measures. Continuous data (e.g. age, BMI,): mean  $\pm$  SD or medians and IQR (depending on normality). Categorical data (e.g. gender, ASA): number and frequencies will be reported for treatment groups.

The quantitative variables obtained from the clinical evaluation (HHS, HOOS, EQ-5D, Oxford Hip Score and Forgotten Joint Score) will be tabulated and analysed as mean, standard deviation, minimum and maximum values. Complications and other clinical relevant information will be documented as known variables. All outcomes will be reported with 95% confidence intervals.

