### **Primary and Secondary Endpoint Analysis**

Analysis for primary and secondary endpoints will use the patient population which consists of those cases with complete data for one or more of the primary and secondary endpoints.

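### No interval method is named for two-year prosthesis survival, and the standard Kaplan-Meier intervals are zero-width or undefined if an arm of 25 has no events

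*Combined protocol and SAP*

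**What the plan says.** The synopsis (Study Objectives/Endpoints) lists as a secondary endpoint "Survival of the hip prosthesis within 2 years". The method is Kaplan-Meier, named in the synopsis row on statistical reporting and again in the Survivorship section, whose whole text is "Hip prosthesis survivorship will be assessed using a Kaplan-Meier analysis". The Descriptive analysis section adds "All outcomes will be reported with 95% confidence intervals". The sample size row gives "50 subjects in total, 25 study subjects implanted with the study device per cohort".

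The documents do not state a variance formula or transformation for the survival interval, what is reported when an arm has no events, an expected revision rate, or which event ends prosthesis survival.

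**The concern.** The standard Kaplan-Meier interval takes its width from the Greenwood variance, which is built from the observed events. With no events it is zero. An analyst who follows the plan by the usual route would then either print 100% survival with an interval of 100% to 100%, or get no interval. The first claims certainty from 25 subjects, and the error favours the device. The second breaks the plan's own promise of an interval. Choosing another method once the zero count is known would be a post hoc decision, on an endpoint that the sponsor or its designee analyses.

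**Working it through.** **Inputs from the documents.** 25 subjects per arm (synopsis, sample size); a two-year horizon (synopsis, endpoints); 95% intervals (Descriptive analysis); two-sided testing at 0.05 (Statistical Method). The plan states no survival figure or interval to reproduce.

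**Assumptions.** The true two-year event risk p is not given, so a range is shown. It is taken as equal in the two arms, with independent subjects and full follow-up. The dropout rate is not given either, so 20 to 25 subjects per arm followed to two years is used as a range.

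**Step 1: the standard intervals with no events.** Greenwood: Var(S) = S² × Σ d/[n(n − d)]. With d = 0 throughout, S = 1 and the sum is 0.

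- Plain: 1 ± 1.96 × 0, giving 100% to 100%.
- Log: the standard error of log S is √0 = 0, so the limits are 1 × exp(±0), again 100% to 100%.
- Log-log: this needs log(−log 1) = log 0, which does not exist.

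Changing the transformation therefore does not help at zero events.

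**Step 2: what 0/n supports.** The exact (Clopper-Pearson) two-sided 95% lower limit for survival with no events is 0.025^(1/n).

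| Followed to two years, no events | Lower limit for survival | Upper limit for event risk |
|---|---|---|
| 25 | 0.025^(1/25) = 86.3% | 13.7% |
| 23 | 85.2% | 14.8% |
| 22 | 84.6% | 15.4% |
| 20 | 0.025^(1/20) = 83.2% | 16.8% |

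**Step 3: how often an arm would be empty.** P0 = (1 − p)^25 for a given arm, and 1 − (1 − P0)² for at least one of the two.

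| Assumed p | A given arm has none | At least one arm has none |
|---|---|---|
| 1% | 0.99^25 = 0.778 | 1 − 0.222² = 0.951 |
| 2% | 0.98^25 = 0.603 | 0.843 |
| 3% | 0.467 | 0.716 |
| 5% | 0.95^25 = 0.277 | 0.478 |
| 10% | 0.90^25 = 0.072 | 0.138 |

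The break-even points are:

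- A given arm is more likely than not to be empty if p < 1 − 0.5^(1/25) = 2.7%.
- For at least one arm, solve 1 − (1 − P0)² = 0.5. This gives P0 = 1 − √0.5 = 0.293, so p < 1 − 0.293^(1/25) = 4.8%.

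**Step 4: one event, as a boundary check.** At 1/25, S = 0.96 and the standard error is √(0.96 × 0.04/25) = 0.0392. The plain interval is 88.3% to 103.7%, the log-log interval 74.8% to 99.4%, and the exact interval 79.6% to 99.9%. From one event on, a standard interval that stays within range is available. The failure is specific to zero events.

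**The case against.** The strongest reply is that the plan contains no wrong method. Kaplan-Meier is a point estimator, Greenwood is never mentioned, and an exact interval around a Kaplan-Meier estimate would comply with the text as written. That stands. A reader might infer that the plan has chosen a faulty interval, and the documents do not support that. The gap is that no method is named, while the usual ones fail in a foreseeable case.

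The promise of intervals closes a paragraph on clinical scores and complications, and the Survivorship section has no such promise of its own. Applying it to survival is reasonable, since it speaks of all outcomes, but it is not certain. If it does not apply, the endpoint has no planned measure of precision, and the same repair is needed.

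A reader might also infer that an empty arm is simply to be expected. The documents do not support that either. They give no revision rate, at 5% the chance for at least one arm is already just under one half, and at 10% it is 14%. Nor do they define the event. The calculation treats it as revision, and a broader event would make zero counts rarer.

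It is also tempting to extend the criticism to an arm with one event. That holds only for the plain interval, which the plan does not choose. The log-log lower limit at 1/25 is below the exact one, so it does not flatter the device.

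Finally, the consequence is limited. The primary endpoint is RSA migration, no decision rule uses the survival interval, a 100% to 100% interval is visibly degenerate, and the Study Safety section separately summarises adverse events leading to removal or revision. This keeps the point minor but does not supply the missing interval.

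**Conclusion.** The point holds as a minor one on a secondary endpoint. With no events in an arm, the standard Kaplan-Meier intervals are zero-width or undefined, whereas 25 subjects followed to two years support only 86.3% to 100%, and 20 subjects only 83.2% to 100%. A printed 100% to 100% would hide an event risk of up to 13.7% or 16.8%. These results need no assumed revision rate.

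How often the problem would arise does depend on assumptions: equal risk in both arms, full follow-up, and revision as the event. On those terms, at least one empty arm is more likely than not only if the true two-year risk is below about 4.8%, and a given arm only below about 2.7%. The choice of Kaplan-Meier is not in error, and the primary analysis is not affected.

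**What to change.** Keep the Kaplan-Meier curve. Add to the Survivorship section, before the data are analysed, a sentence to this effect: two-year survival will be reported for each arm with the number at risk at two years and a two-sided 95% exact-type interval, by Clopper-Pearson if all subjects in the arm complete two years and by the beta product confidence procedure if any are censored earlier. The rule applies whatever the event count and whichever event is counted, so nothing is left to decide after seeing a zero.

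The plan specifies no between-arm survival contrast, and none is needed to close this gap. If the sponsor wants one, a Newcombe or Miettinen-Nurminen interval for the difference is usable at zero events (0/25 against 0/25 gives about −13.3% to +13.3% by Newcombe), but only with complete follow-up, because both treat the arms as simple proportions.

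The cost is one sentence and a few lines of code. The interval will be wider and less favourable, and the beta product procedure may need software other than the package the plan names. Clopper-Pearson with no events needs only the formula shown in the working.

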### **Study Safety**

All adverse events will be recorded, described, and compared for the groups. Comparisons will use standard statistical tests (chi-square, Fisher’s exact). Adverse events resulting in device removal and/or revision and those not requiring device removal and/or revision will be summarized. Device related serious adverse events will be collected and evaluated for differences in the population.
